## 9.3.4 Interim Monitoring

Interim efficacy monitoring on the incidence of bacteremia will be performed twice when data is available for approximately one-third and two-thirds of patients (separately for AL patients and HSCT patients). Monitoring boundary will be based on Lan-Demet's method with spending function  $\alpha t^2$ . Futility analyses based on conditional power will also be performed at the same time separately for each patient group. The probability of establishing efficacy of levofloxacin given the currently observed data will be calculated. In calculating the conditional power, the outcome for future patients will be assumed to follow the alternative hypothesis. If the conditional power falls below 10%, it will be considered evidence that it is unlikely to establish efficacy of levofloxacin in the particular patient group at the end of the study. The data will be referred to the COG Data Safety and Monitoring Committee (DSMC) for consideration of early termination for the particular patient group. Accrual will not be suspended for these interim monitoring and analyses. The incidence of musculoskeletal disorder will be monitored between the 2 arms by descriptive statistics and Fisher's exact test at each interim DSMC report, which occurs approximately every 6 months during the first 2 years and annually thereafter. For tendon rupture, as concurrent steroid use is considered a risk factor, the analysis will also be considered separately for levofloxacin patients with/without concurrent steroid use or with adjustment for steroid use. A previous report on > 2,500 patients found a small increase in the musculoskeletal disorder incidence (3.4% versus

1.8%) in levofloxacin treated patients; however our study is not powered to detect a difference of this magnitude. Therefore, the monitoring on incidence of musculoskeletal disorder will be informal and mainly for safety reassurance. Such safety monitoring will always be done at marginal alpha level of 0.05 and not adjusted for the multiple comparisons. If any such safety comparison suggests a significantly higher incidence of musculoskeletal disorder for levofloxacin, the study committee will carry out a review of the observed disorders; the results and any committee recommendation will be reported to the DSMC. The DSMC may also have its own assessment and recommendation about musculoskeletal event safety given the observed data.

## 9.4 Gender and Minority Accrual Estimates

Per Amendment #3, the study targets to enroll 666 eligible and evaluable patients (266 AL patients and 400 HSCT patients), with a maximum enrollment of 740 patients. The gender and minority distribution of the study population is expected to be:

Accrual Targets						
Ethnia Catagony	Sex/Gender					
Ethnic Category	Females	Males	Total			
Hispanic or Latino	73	97	170			
Not Hispanic or Latino	240	330	570			
Ethnic Category: Total of all subjects	313	427	*740			
Racial Category						
American Indian or Alaskan Native	2	1	3			
Asian	12	13	25			
Black or African American	44	45	89			
Native Hawaiian or other Pacific Islander	0	5	5			
White	255	363	618			
Racial Category: Total of all subjects	313	427	*740			

\* These totals must agree

This distribution was derived from AAML0531, AALL01P2, POG-9411, ASCT0431 and ACCL0331. The first 3 studies were used to generate an estimated distribution for AL patients; the last 2 studies were used to generate an estimated distribution for HSCT patients. The overall distribution was estimated based on a 1:1 mixture of the estimated AL and HSCT distributions.

#### 9.5 Resistance Surveillance Statistical Considerations

## 9.5.1 Ancillary Study Aims

# 9.5.1.1 Primary Aim

To determine whether prophylactic levofloxacin versus no levofloxacin is associated with an increased risk for the development of gastrointestinal colonization with certain antimicrobial resistant organisms. The following resistance scenarios will be analyzed first as a group and then 1-by-1:

- 1a. Levofloxacin resistance among E. coli, K. pneumoniae, P. aeruginosa and S mitis
- 1b. Cefepime resistance among E. coli, K. pneumoniae, P. aeruginosa and S mitis
- 1c. Imipenem resistance among E. coli, K. pneumoniae, and P. aeruginosa
- 1d. Penicillin resistance among *S mitis*

The above aim identifies 12 bacteria-antibiotic combinations for organisms to be identified from the gastrointestinal tract. The primary hypothesis for this primary aim is that the use of levofloxacin prophylaxis will result in a greater increase from baseline in the number of resistant combinations among these gastrointestinal organisms as compared to patients not receiving levofloxacin prophylaxis. In a sub-analysis, the change in frequency of resistance from baseline for each of the 12 bacteria-antibiotic combinations will be compared between patients in the 2 study arms.

## 9.5.1.2 Secondary Aim

The secondary aim is to determine whether prophylactic levofloxacin versus no levofloxacin is associated with an increased risk for the development of bacteremia or sterile site infection from either Gram positive or Gram negative resistant organisms. The following resistance scenarios will be considered independently:

- 1a. Levofloxacin resistant Gram positive and Gram negative organisms
- 1b. Cefepime resistant Gram positive and Gram negative organisms
- 1c. Imipenem resistant Gram positive and Gram negative organisms
- 1d. Penicillin resistance for *S mitis* only

The secondary hypotheses for these secondary aims are that the use of levofloxacin prophylaxis is associated with an increased risk of infection with levofloxacin resistant Gram positive as well as Gram negative organisms. Additionally, exposure to levofloxacin prophylaxis results in an increased risk of infection with both Gram positive and Gram negative organisms resistant to cefepime and imipenem. Lastly, levofloxacin prophylaxis is associated with an increased risk of penicillin resistant *S mitis*.

## 9.5.1.3 Tertiary Aim

The tertiary aim is to describe the frequency of stool colonization with a carbapenem-resistant Enterobacteriaceae in patients that have received prophylactic levofloxacin versus those that did not.

As this aim only plans to describe the frequency of carbapenem resistant Enterobacteriaceae there is no formal hypothesis.

## 9.5.2 Statistical Design for Ancillary Study

Factors that can potentially impact the analysis of the primary aim of the ancillary study include total days and class (carbapenem, cephalosporins, etc) of antibiotic exposure (other than the study drug). These will be compared across the two study arms and accounted for in all analyses related to the resistance aims. The adjusted analyses will be exploratory in nature.

#### 9.5.2.1 Preliminary Descriptive Analysis

The initial analysis will involve describing the distribution of data. Specific demographic data will be characterized as described in the parent trial. We will additionally, characterize both groups (levofloxacin prophylaxis and no prophylaxis) by frequency of resistance to each antibiotic of interest for each of the gastrointestinal colonizing organisms, by frequency of resistance to each antibiotic of interest for both Gram positive and Gram negative infecting organisms, and by the amount of concomitant broad spectrum antibiotic utilization in addition to prophylactic levofloxacin (reported by class of antibiotics as an index of days of antibiotics per hospitalization days).

## 9.5.2.2 Comparative Analysis for the Primary Aim

The proposed study essentially represents a parallel safety study of the use of prophylactic levofloxacin in the setting of fever and neutropenia. As such it seeks to estimate the impact of such prophylaxis on the

evolution of resistance among gastrointestinal colonizing organisms (primary aim) and infecting organisms (secondary aim) as an important safety issue.

As an initial simple test of association of levofloxacin prophylaxis and the development of gastrointestinal resistance between the two study arms, we shall compute the change in the number of resistant combinations identified for a patient after the intervention or standard care as compared to their baseline count. The potential range for the difference from post intervention to baseline is from -12 to 12. The mean change in resistance combinations will be compared between the two study arms using the student's t-test. In the event that this change is not normally distributed a non-parametric approach will be performed utilizing the Mann-Whitney U test. The comparison in the change in resistance combinations will be done at the completion of the first course of prophylaxis or standard of care for all patients in the study. For children with AL, prophylaxis or standard care will continue through a second period of neutropenia. Therefore, the change in resistance combinations after this second period of neutropenia will be compared to baseline for AL patients only, again using the student's t-test.

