#### 1.2.2

To determine the effect of levofloxacin prophylaxis on total number of days of antibiotic administration (prophylactic, empiric and treatment) in children undergoing therapy for AL and HSCT.

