#### 9.0 STATISTICAL CONSIDERATIONS

## 9.1 Statistical Design

This study is a randomized trial to investigate the effect of levofloxacin on preventing bacteremia in children being treated for AL or undergoing HSCT. Patients will be randomized between levofloxacin and no levofloxacin during 2 consecutive cycles of chemotherapy for AL or during 1 HSCT. Randomization will be stratified by 4 groups: 1) *de novo*, secondary or relapsed AML or acute leukemia of ambiguous lineage treated with standard AML therapy; 2) relapsed ALL; 3) autologous stem cell transplantation; 4) allogeneic stem cell transplantation. The study is designed to analyze AL and HSCT patients separately.

The primary aim is to determine the effect of levofloxacin on the incidence of bacteremia during the study timeframe of 2 cycles of chemotherapy or 1 transplant procedure among AL and HSCT subjects respectively. Besides assessing the safety of levofloxacin, especially on musculoskeletal disorders, other secondary aims are to determine the effect of levofloxacin on: total days of antibiotic administration, incidence of fever with neutropenia, incidence of severe infection, incidence of death from bacterial infection, incidence of CDAD, incidence of IFI, resistance patterns of bacterial isolates from sterile site cultures, evolution of antimicrobial resistance from stool or peri-rectal swab isolates of *E. coli, K. pneumoniae, P. aeruginosa* and S. *mitis* and presence of stool colonization by carbapenem-resistant Enterobacteriaceae.

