## 9.3.3 Analysis Plans

All primary analyses will be performed separately for AL and HSCT patients, and all primary analyses involving treatment effect will be intent-to-treat (ITT).

The primary outcome is the incidence of bacteremia during the study period. Within either patient cohort, we will compare the incidence of the bacteremia between the 2 randomized arms using the Chi-square test. If within either patient group the data suggest a possible difference in baseline incidence between the

2 randomization strata, we will consider Cochran-Mantel-Haenszel test to examine the association between the incidence of bacteremia and the study treatment with adjustment for the randomization strata; Breslow-Day test for homogeneity in odds ratio across the strata will also be considered. Logistic regression models will be performed to evaluate the treatment effect on the incidence of bacteremia adjusting for stratification and other baseline patient characteristics. Logistic regression models combining AL and HSCT patients will also be performed to evaluate the effect of levofloxacin on bacteremia in the two patient groups, and a test for interaction between treatment and patient group will be performed to examine if treatment effect differs between the two patient groups.

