## 9.5.2.3 Secondary Analysis for the Primary Aim

Although the parent study (on effectiveness of levofloxacin prophylaxis) will utilize standard principles of intent-to-treat analysis, those principles may be at odds with the goal of estimating the negative effects (resistance) of prophylaxis. Drop-out from the parent study might reduce power but be uninformative and unrelated to the eventual parent study outcome (incidence of bacteremia). In contrast, drop-out in this ancillary study might be acutely informative by being related to the emergence of an adverse event such as the development of infection due to resistant organism. Second, although randomization at baseline should balance all differences between the treatment groups by measured and unmeasured confounders, extra precautions are needed to guard against the potential bias of baseline covariates with chance imbalance from finite sample sizes. Additionally, there may be nonrandom assignment to additional antibiotics, and those post-randomization exposures might also bias results if they are not properly controlled. Finally, there is no guarantee that the subjects who enter the study will not carry resistant organisms at the time of initial enrollment. The presence of future carriage of resistant organisms by an individual is likely related to the presence of or absence of colonization at or prior to initiation of antimicrobial prophylaxis.

To address these issues, we propose a multivariate mixed-effects analysis that accounts for drop-out, variation in baseline covariates, and variation in post-randomization exposures (e.g. additional antimicrobials). A multivariate mixed-effects model has the versatility to be expanded to account for confounding from drop-out, covariate inequities from finite sample size, and administration of other antibiotics in addition to the prophylactic antimicrobials. For this model the multivariate outcome will be the 12 dichotomous outcomes (0 for no resistance and 1 for resistance) for each of the bacteria-antibiotic combinations. The model will account for the lack of independence of outcomes for each subject within a given measurement time, as well as the correlation of repeated measures over time. This multivariate mixed-effect model will attempt to assess the true causal effect of prophylactic levofloxacin on the risk of overall resistance among colonizing organisms.

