## 9.5.2.4 Comparative Analyses for the Secondary Aim

Unlike the outcome for the primary aim which will be obtained at fixed timepoints, the outcomes for this secondary aim (positive sterile site culture with a resistant organism) will be present at varying times from study enrollment. Therefore, we propose a Cox proportional hazards regression model that will be adapted to address issues of concomitant nonrandomized treatment (time-dependent confounding), and informative drop-out. Each outcome (presence or absence of resistance for the specified group of infecting organisms and antibiotic) will be evaluated in separate models.

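### The powered resistance t-test leaves baseline count and strata out of the model, and the only baseline-adjusted analysis also adjusts for antibiotics given after randomization under a causal-effect label

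*Combined protocol and SAP*

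**What the plan says.** **Powered comparison (9.5.2.2).** The plan counts resistant bacteria-antibiotic combinations per patient (12 possible) and takes the change from baseline. "The mean change in resistance combinations will be compared between the two study arms using the" Student's t-test, with Mann-Whitney as the fallback for non-normal change. The first comparison pools all AL and HSCT patients after course one; the second uses AL patients only, after course two. Neither has a covariate. The test is presented as a first, simple one, but the power statements in 9.5.3.2 are built on it.

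**Strata (9.1).** "Randomization will be stratified by 4 groups": AML, relapsed ALL, autologous HSCT and allogeneic HSCT.

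**Secondary model (9.5.2.3).** The plan gives a reason to use baseline: "The presence of future carriage of resistant organisms by an individual is likely related to the presence of or absence of colonization" at or before the start of prophylaxis. It then proposes a multivariate mixed-effects model of the 12 binary outcomes that "accounts for drop-out, variation in baseline covariates, and variation in post-randomization exposures (e.g. additional antimicrobials". That model "will attempt to assess the true causal effect of prophylactic levofloxacin on the risk of overall resistance among colonizing organisms".

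**Secondary aim (9.5.2.4).** The Cox model for sterile-site infection is to be "adapted to address issues of concomitant nonrandomized treatment (time-dependent confounding" and informative drop-out. Section 9.5.2.3 has no matching statement of method.

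**General rule (9.5.2).** Antibiotic exposure other than study drug is to be allowed for in every resistance analysis. The next sentence calls the adjusted analyses exploratory.

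**The concern.** There are two gaps, and they are linked.

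First, baseline swabs and strata are already collected, and the plan itself expects baseline carriage to predict later carriage. Subtracting the baseline count is not the same as conditioning on it: subtraction fixes the baseline slope at 1, whatever the data show.

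Second, the analysis that does try to deal with baseline carriage brings in a variable that lies downstream of randomization. Objective 1.2.2 is "To determine the effect of levofloxacin prophylaxis on total number of days of antibiotic administration", and it includes empiric and treatment days. (It includes prophylactic days too, so that outcome and the adjustment variable overlap without being identical.) Objective 1.2.3(a) asks whether levofloxacin reduces fever with neutropenia, which 4.1.1 gives as its example of why parenteral antibiotics are started. If prophylaxis works as hypothesised, other antibiotic use is partly its consequence.

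Taken together, no listed analysis conditions on baseline and strata without also accounting for post-randomization antibiotics. Section 9.5.3.2 makes colonization the main resistance endpoint because resistant infections will be too few. A reader could therefore take the model with the causal wording as the definitive safety answer on resistance.

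**Working it through.** **1. Reproduce the plan's power.** Inputs from 9.5.3: change SD 3.0; 266 per arm, difference 1.0; 106 AL patients per arm, difference 1.25. Section 9.5 gives no alpha, so two-sided 0.05 is assumed from the parent trial (9.3.2). Noncentral t with noncentrality = difference / (3.0 × √(2/n)):

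- 266 per arm: 1.0 / (3.0 × √(2/266)) = 3.84, power 97.0% (plan: 97%).
- 106 per arm: 1.25 / (3.0 × √(2/106)) = 3.03, power 85.5% (plan: 0.86).

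Both reproduce. A one-sided test would give about 92% for the second, so two-sided is the consistent reading.

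**2. Effect of conditioning on the baseline count.** Let ρ be the baseline-to-post correlation and k the ratio of post SD to baseline SD. The documents give neither, so both are assumed, and the change SD is held at 3.0. The variance of the adjusted estimate relative to the t-test is

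k²(1 − ρ²) / (k² + 1 − 2kρ).

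Example, k = 1 and ρ = 0.2: 0.96 / 1.60 = 0.600. The adjusted SD is 3.0 × √ratio. Each cell shows the variance ratio, then AL power at 106 per arm and difference 1.25:

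| k | ρ = 0.2 | ρ = 0.3 | ρ = 0.5 | ρ = 0.7 |
|---|---|---|---|---|
| 1.0 | 0.600; 97.4% | 0.650; 96.3% | 0.750; 93.7% | 0.850; 90.6% |
| 1.5 | 0.815; 91.7% | 0.871; 89.9% | 0.964; 86.8% | 0.998; 85.6% |
| 2.0 | 0.914; 88.5% | 0.958; 87.0% | 1.000; 85.5% | 0.927; 88.0% |
| 2.5 | 0.960; 86.9% | 0.989; 85.9% | 0.987; 86.0% | 0.850; 90.6% |

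The gain vanishes when kρ = 1, because subtraction is then already optimal. For all patients (266 per arm), the difference detectable with 80% power is 0.73 with the t-test and 0.57 to 0.73 after conditioning.

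**3. Cost if the terms predict nothing.** At 106 per arm with two extra terms the variance rises by a factor of about 1.010, and power goes from 85.5% to 85.2%.

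**4. Behaviour with skewed counts.** Simulation: negative binomial counts capped at 12, 106 per arm, 1,500 runs per scenario, model with baseline count, one stratum term and HC3 standard errors. All scenario means are assumed.

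- Type I error: 4.4% to 5.5% for the t-test, 4.5% to 5.5% for the model.
- Baseline mean 1.5, post mean 1.5 to 2.25: the model gains 3 to 9 points of power at a shift of 0.8.
- Baseline mean 0.3 to 0.5, post mean 1.0 to 2.0: power changes by −1.3 to +0.1 points, so no gain.

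**5. Adjusting for post-randomization antibiotics.** For a linear model, total effect = direct effect + effect passing through other antibiotics. Ordinary covariate adjustment removes the second part. It can also bring in bias through unmeasured causes of both antibiotic use and resistance.

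A simulation shows the mechanism. Assumptions: levofloxacin lowers antibiotic use by 0.4 SD, an unmeasured cause affects both antibiotic use and resistance, antibiotics have no effect on resistance, and the true difference is 1.0. The unadjusted comparison averaged 1.00 and the antibiotic-adjusted one 1.20. The 0.4 SD is borrowed from 9.3.2, where it is a detectable AL difference in parenteral days, not an expected one. This is not a forecast.

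**The case against.** **The t-test is valid and adequately powered.** This stands in full. A reader might infer that the powered comparison is biased or underpowered. It is not: randomization protects it, the stated power reproduces, and the gain from conditioning rests on ρ and k, which nobody knows yet. The aim concerns development of colonization; if baseline counts are low, there may be no gain.

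**The parent trial does much the same.** It is tempting to say that the parent trial adjusts for strata while the ancillary study does not. Section 9.3.3 does not support that contrast. Its first-line test is an unadjusted Chi-square, Cochran-Mantel-Haenszel is only conditional, and the logistic models that "evaluate the treatment effect on the incidence of bacteremia adjusting for stratification and other baseline patient characteristics" come in addition.

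**Baseline carriage is not ignored.** Also right. The change score uses it, and 9.5.2.3 lists carriage at enrolment among the issues its model is meant to address. What is missing is an analysis that does this without the post-randomization terms.

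**The different estimand is deliberate.** Section 9.5.2.3 says intent-to-treat principles may conflict with estimating harm, and an effect with other antibiotics controlled is still a causal quantity. The t-test already estimates the total effect. This has force, and it is why the antibiotic-adjusted model should stay. But the section states neither which effect is targeted nor how time-varying exposure is handled. Its wording refers to the effect of levofloxacin without qualification.

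**The method is left open.** A reader might infer that the mixed model is certainly biased. The documents do not settle that: the problem arises with ordinary covariate adjustment, which 9.5.2.3 neither specifies nor rules out.

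**Conclusion.** The point holds as a recommended improvement, not as an error that invalidates an analysis.

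- **Baseline and strata.** Conditioning on them costs about 0.3 points of AL power at worst. Under the assumed ρ of 0.2 to 0.7 and k of 1 to 2.5, with change SD 3.0, AL power is 86% to 97% against 86%. Little or no gain should be expected if resistance mostly emerges on study.
- **Causal wording.** If post-randomization antibiotics enter as ordinary covariates, the mixed model does not estimate the total effect of assigning prophylaxis. The size and direction of the gap cannot be determined from the documents. It is zero if levofloxacin does not change other antibiotic use and the adjustment opens no unmeasured common cause. The wording is also out of step with 9.5.2, which calls adjusted analyses exploratory.
- **Scope of adjustment.** A reader might see a serious contradiction between 9.5.2, which extends adjustment to every resistance analysis, and the unadjusted test in 9.5.2.2. Because 9.5.2 at once calls the adjusted analyses exploratory, this is a wording clean-up.

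**What to change.** 1. **Section 9.5.2.2.** Make the main test a linear model of the post-course count on arm, baseline count and randomization strata, with robust standard errors. For the second-course AL test, use only the AML and relapsed ALL strata. Keep the t-test and the Mann-Whitney test as supporting analyses.
2. **Section 9.5.2.3.** Fit the mixed model without post-randomization antibiotics for the total effect, with strata as named terms. Handle baseline resistance once: either as a covariate with post-baseline outcomes only, or as a repeated outcome with an arm-by-time effect. Doing both would use the baseline swab twice. Keep the antibiotic-adjusted version as exploratory, state its estimand and its method for time-varying exposure (the reference list already contains a marginal structural model paper), and remove the causal-effect label from it.
3. **Section 9.5.2.** Replace the blanket statement about adjustment with a list of the analyses that are adjusted, so that it agrees with 9.5.2.2.

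The cost is SAP wording and some extra model fits. Baseline swabs, strata, and antibiotic names with start and stop dates (7.1.2.1) are already collected.

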## 9.5.3.2 Event Rates for Power Calculations

Contemporary data are limited on the frequency at which colonizing organisms can be isolated from stool or peri-rectal swabs for each of the organisms of interest. It has been shown in a small study of adult patients with AL, that 31% of patients had *P. aeruginosa* identified on at least 1 stool specimen. However, the goal of this ancillary study is to determine whether the presence of organisms retaining resistance to certain antibiotics are increased above baseline in patients receiving levofloxacin prophylaxis compared to those not receiving prophylaxis. Thus for each swab result, a dichotomous interpretation of each bacteria-antibiotic combination (presence versus absence of the resistant organism) is most appropriate. Interpreting swab results in this way will make the results of all swab specimens informative in the final analysis.

The evolution of resistance for each organism-antibiotic combination of interest is not known, and thus the anticipated mean change in resistance counts from baseline to post-exposure cannot be reasonably estimated for either treatment arm. Instead, we evaluated the power to detect various differences in the mean change of resistance counts between the 2 study groups. Assuming that each study arm will yield 266 (assuming 80% of parent trial patients enroll in this ancillary study) evaluable specimens at baseline and post prophylaxis or standard of care timepoints, then this study will have 97% power to detect a difference between the two study group mean resistance counts as small as 1.0. This power calculation also assumes a substantial standard deviation in the mean of the difference in resistance counts of 3.0. Thus, there is power to detect even a small change in the mean difference of resistance between the two study arms.

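### The first-course resistance comparison can change from the powered test of means to a Mann-Whitney test on an undefined normality condition, and the two tests can disagree

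*Combined protocol and SAP*

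**What the plan says.** The outcome of the ancillary resistance study is a count. Section 9.5.1.1: "The above aim identifies 12 bacteria-antibiotic combinations for organisms to be identified from the gastrointestinal tract". The hypothesis there is that levofloxacin "will result in a greater increase from baseline in the number of resistant combinations among these gastrointestinal organisms". Section 9.5.2.2 takes each patient's change from baseline in that count and notes: "The potential range for the difference from post intervention to baseline is from -12 to 12".

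The test is set in the same section: "The mean change in resistance combinations will be compared between the two study arms using the student's t-test". The next sentence is the switch: "In the event that this change is not normally distributed a non-parametric approach will be performed utilizing the Mann-Whitney U test". No normality test, significance level or graphical rule is named. The text does not say whether normality is judged by arm or pooled, or that the comparison of means is still reported after a switch.

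For acute leukemia (AL) patients, a second comparison follows the second neutropenic period. For that one, 9.5.2.2 names the t-test again and gives no alternative.

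Power is given for means only. In 9.5.3.2, "we evaluated the power to detect various differences in the mean change of resistance counts between the 2 study groups". The results are 97% for a difference of 1.0 with SD 3.0 and 266 per arm, and 0.86 for a difference of 1.25 with about 106 AL patients per arm. The same section says the expected mean change cannot be estimated for either arm.

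**The concern.** The t-test and the Mann-Whitney test answer different questions. The first asks whether the average number of resistant combinations rises more in one arm. The second asks whether a randomly chosen patient in one arm tends to rank above one in the other. The rank test gives little extra weight to a gain of 3 or 6 over a gain of 1.

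The count is built so that gains can come in lumps. One organism newly resistant to all its tested drugs adds 3 combinations. Small losses are also possible: 9.5.2.3 accepts that patients may carry resistant organisms at entry, and 2.3 describes levofloxacin as active against relevant Gram-negative and Gram-positive pathogens. If many children lose one combination and a few gain several, the mean and the ranks can part company.

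Section 9.5.2.2 presents this as a safety study, and 9.5.3.2 makes colonization its primary endpoint because resistant infections will be too few. A rule that lets the data decide which quantity is tested could therefore hide, in this comparison, the harm it is meant to detect.

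**Working it through.** **1. Stated power.** Inputs from 9.5.3.2: 266 per arm, difference 1.0, SD 3.0. Section 9.5 states no alpha, so I assume two-sided 0.05, as in 9.3.2 for the parent trial.

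- SE = 3.0 × √(2/266) = 0.260; 1.0/0.260 = 3.844; power = Φ(3.844 − 1.96) = 0.970. Stated: 97%.
- AL second course: SE = 3.0 × √(2/106) = 0.412; 1.25/0.412 = 3.033; power = Φ(3.033 − 1.96) = 0.858. Stated: 0.86.

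Both reproduce, so both are powers of a comparison of means.

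**2. Will the condition be met?** The count has 4 + 4 + 3 + 1 = 12 yes/no items, so the change is a bounded integer and cannot be exactly normal. Whether a check says so depends on the check and the shape, so I assumed distributions and simulated 266 per arm.

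- Best case (normal, SD 3.0, rounded to integers): Shapiro-Wilk at 0.05 rejected in about 98% of single arms, and in at least one arm in 100% of trials. Jarque-Bera rejected in 5.2% and D'Agostino-Pearson in 5.6%, which is about their nominal level. At 106 per arm, Shapiro-Wilk rejected in at least one arm in 50% of trials.
- Zero-heavy shapes: three normality checks rejected in 99 to 100% of trials.

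**3. Does the t-test need protecting?** I used a zero-heavy null with the same distribution in both arms: changes of -1/0/1/2/6 with probabilities .08/.80/.07/.03/.02. At 266 per arm, two-sided type I error was 5.3% for the t-test and 5.1% for Mann-Whitney. A second zero-heavy null gave 4.2% for the t-test. Non-normality alone does not force a switch at this size.

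**4. Do the tests agree?** All patterns are assumptions, at 266 per arm. Harm means significantly more resistance on levofloxacin.

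| Pattern (control; levofloxacin) | Mean difference | t-test: harm | Mann-Whitney: harm | Mann-Whitney: reduction |
|---|---|---|---|---|
| Plain shift of 1.0, SD 3.0, rounded | 1.0 | 96.8% | 96.0% | – |
| Sparse, shifted up (-1/0/1/2: .10/.75/.10/.05; -1/0/1/2/3/4: .10/.60/.12/.08/.06/.04) | 0.42 | 100% | 95.6% | 0% |
| Gains of exactly 3 (-1/0/1: .08/.82/.10; 18% lose 1, 14% gain 3) | 0.22 | 83% | 0.1% | 18% |
| Gains of 4 to 6 (-1/0/1: .10/.78/.12; 20% lose 1, 12% gain 4 to 6) | about 0.38 | 96% | under 0.1% | 47% |
| Gains of 5 or 8 (-1/0/1: .10/.70/.20; -1/0/5/8: .12/.70/.12/.06) | 0.86 | 100% | 2.9% | 2.2% |

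The third row can be checked by hand, with T for levofloxacin and C for control.

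- Means: 3 × 0.14 − 0.18 = 0.24 against 0.10 − 0.08 = 0.02, a rise of 0.22.
- Ranks: P(T>C) = 0.14 + 0.68 × 0.08 = 0.194.
- Ranks: P(T<C) = 0.18 × 0.92 + 0.68 × 0.10 = 0.234.

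The mean says more resistance and the ranks say less.

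**The case against.** **The switch is not certain.** A reader might infer that any normality check must reject, because the outcome is an integer. The documents do not support that. They name no check, and 9.5.3.2 plans on SD 3.0. With a bell-shaped change of that spread, two of the three checks reject only at their nominal rate, and a histogram would probably pass. This stands. What remains is that the criterion is undefined and that a zero-heavy count would very likely trigger the switch.

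**Both power figures are not lost.** A reader might infer that the 97% and the 0.86 both belong to a discarded test. The 0.86 is for the AL second-course comparison, where 9.5.2.2 names only the t-test, so it is unaffected. The 97% is at risk only if the switch occurs, and a plain shift then loses less than one point.

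**The hypothesis does not name a mean.** Section 9.5.1.1 speaks of a greater increase in a number, which a rank comparison could also address. That is fair. The commitment to the mean comes from the test in 9.5.2.2 and the power in 9.5.3.2.

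**Reversal rests on chosen patterns.** Each organism supplies at most 3 of the 12 combinations, so gains of 4 to 6 need at least two newly resistant species in one course, and 9.5.2.5 expects carbapenem-resistant commensals to be few. With a control of 10% losing 1, 80% unchanged and 10% gaining 1, against 20% losing 1 and 30% gaining 1 to 3, Mann-Whitney found harm in 74% of trials and never reversed. This limits how likely reversal is, but does not remove it: the third row of the table needs only one fully resistant organism per affected child.

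**Other analyses exist.** The test is described as an initial, simple one in an optional study. Each of the 12 combinations is also compared between arms (9.5.1.1), and a mixed-effects model of the 12 binary outcomes, which the normality condition does not touch, follows as a secondary analysis (9.5.2.3). So the documents do not support inferring that the whole study would report a reduction; the risk is to this comparison.

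**Conclusion.** The point holds for the first-course comparison. As written, the analysis can move from the comparison of means, the only one with stated power, to a test of a different quantity, on a condition that is undefined and judged after the data are seen. The move is very likely if the changes are mostly zero and uncertain if they are bell-shaped with SD near 3.0.

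The consequence depends on a distribution that the documents say cannot be anticipated. Under a plain shift it is negligible (96.8% against 96.0%). Under the assumed mixed patterns, Mann-Whitney detected a mean rise in resistance in at most 2.9% of trials where the t-test did so in 83 to 100%, and it was significant for a reduction in 2.2% to 47%. These figures show what can happen; they do not forecast it.

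Because the alternative is written for the first course only, the two time points could also be analysed on different scales. The point is worth correcting, but it does not threaten the parent trial, and the other planned resistance analyses limit the harm.

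**What to change.** In 9.5.2.2, delete the normality condition. State that the difference between arms in mean change, with its 95% CI, is the analysis after the first course for all patients and after the second course for AL patients, whatever the distribution looks like. Use a Welch t-test or a permutation test of the mean. Keep Mann-Whitney as a sensitivity analysis at both time points, and explain any disagreement by showing the distribution of changes in each arm. State alpha and sidedness in 9.5, which now gives neither.

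The cost is a sentence or two of text. No data collection or sample size changes, and the stated powers of 97% and 0.86 then describe the analyses that will be run.
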